7.1 Description of the individual phases of the study process

7.1.1 Information and consent

- Each subject is informed about the nature, significance, objectives, possible risks, expected benefits, implications and other aspects of the study through a discussion between the investigator and the subject. The subject receives written information about the EIT study. The investigator makes sure that the subject has understood the information. After the clarification, each subject is given enough time and opportunity to clarify open questions and to decide on his or her participation.
- Each subject signs and dates his or her consent to participate in the study in writing on the consent form. The consent also explicitly refers to the collection and processing of personal data. Therefore, the subjects are explicitly informed about the purpose and scope of the collection and the use of these data, especially health data.
- One copy of the signed consent form (copy or 2nd original) is given to the subject, the other remains at the trial centre.
- The proband may withdraw consent and discontinue the examination or terminate the study at any time and without giving reasons. In such cases, the proband is asked to state the reason for discontinuation (for the treatment or participation), but is advised that he/she does not have to do so. The time of withdrawal of consent to treatment or study shall be documented.
- Information and consent about planned publication of data

7.1.2 Randomisation

- not applicable

7.1.3 Treatment phase

- not applicable

7.1.4 Examinations in the context of discharge

- not applicable

7.1.5 Follow-up examinations

- not applicable

7.2 Description of the individual visits

- not applicable

7.3 Description of laboratory and other examinations and methods

EIT is a radiation-free non-invasive imaging procedure that provides a special view into the lungs. In a cross-sectional projection, the distribution of the respiratory volume in the thorax is displayed.

In this representation, ventilated and non-ventilated areas of the lung can be seen, as well as their changes depending on time.

7.4 End of study participation

The regular end of study participation for each participant: Completion of the EIT investigation.

7.4.1 Premature withdrawal of a patient from the study (discontinuation criteria)

Participation in the EIT investigation is voluntary. Each participant has the right to withdraw from the study prematurely at any time at his or her own request and without giving reasons (consent is withdrawn) or to decide to discontinue the study (no further EIT study) without incurring any disadvantages.

Should a participant withdraw consent and drop out of the study, this constitutes a discontinuation of participation. The participant is asked to state the reason for dropping out, but is advised that they do not have to do so. It will be documented that, when and, if applicable, why he/she withdrew his/her consent.

7.4.2 Procedure after (early) departure

Deleting the EIT data on the machine

7.5 End of the study

7.5.1 Regular end of studies

The study participation ends regularly for each study participant after completion of the EIT examination.

7.5.2 Early study end/termination of the entire study

Possible reasons for premature termination of the entire study are:

- Inadequate recruitment rate

The decision to discontinue the study is made by the study director and his/her deputy.

8. adverse events

8. 1 Possible complications and/or risks

- Side effects known so far: none known and published so far, pressure points on the skin are possible due to the EIT belt, because the examination is performed lying down with the upper body elevated by 30°.
- study-specific complications:
None to be expected, as non-invasive and radiation-free examination
In all studies published so far on EIT, especially in the field of intensive care, no complications have been described.

8.2 Recording and documenting adverse events

- none are to be expected, as none have been described in the literature so far and are not to be expected by the nature of the investigation.

9. biometrics

9.1 Endpoints

9.3 Planning the scope of the study (caseload planning)

Considering the first comparison of EIT data of spontaneously breathing lung-healthy subjects compared to patients with dyspnoea in the context of a post-COVID syndrome, a subject number of n=80 and patient number of n=20 each is assumed to be sufficient for the investigation of significant differences. The number of subjects is planned to be higher than the number of patients so that enough reference values of EIT in the different age groups can be analysed and compared with those of the patients in the age-adjusted comparison.

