1.3 Synopsis

Title of the study	Visualisation of changes in regional ventilation in dyspnoeic post-COVID patients - a case-control study using electrical impedance tomography
Acronym	ViReVentPoCov
Director of Studies	Dr. med. [name]
Deputy of the Director of Studies	Priv.-Doz. Dr. med. habil. Dr. [name]
Indication/target population/disease	Post-COVID patients and reference group of lung-healthy subjects
Study design/methodology	
 - monocentric - not controlled; type and number of control groups: 1 - Case-control study (retrospective patient data from routine treatment vs. reference group)
Aims of the clinical trial/objectives	
Primary objective: Examine whether post-COVID patients with dyspnoea show changes in regional ventilation compared to a reference group of lung-healthy subjects.
 
Secondary objectives: To review the indication of EIT in post-COVID patients with dyspnoea.

Study objective	
Primary target figure/main target criterion: There is a difference in regional ventilation between healthy lung patients and post-COVID patients with dyspnoea.
 
Changes in the configuration of the minute image and the regional ventilation delay (RVD) image, the RVD diagram and video-based analysis of the dynamic images
 
Secondary target variables/ secondary target criteria: Review of the indication for an EIT examination in patients with post-COVID syndrome

Number of patients	
Number in analysis: n=20 post-COVID patients / n=80 healthy lung patients
 
Considering the first comparison of EIT data of post-COVID patients with those of a reference group, no formal calculation of the number of patients is calculated and a patient number of n=20 and a subject number of n=80 are assumed to be sufficient. The number of subjects is planned to be higher than the number of patients so that enough reference values of EIT in the different age groups can be analysed and compared with those of the patients in the age-adjusted comparison.

Inclusion criteria	EIT data of post-COVID patients with dyspnoea from the post-COVID outpatient clinic of university hospital Jena (retrospective) and lung-healthy non-smokers without resting or exertional dyspnoea (both groups breathing spontaneously).
Exclusion criteria	
 - Pacemaker - BMI over 50, here the PulmoVista® 500 system should not be used according to the manufacturer. - uncontrolled body movements

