4.5 Patient recruitment

- Accessibility of the intended number of patients:
- Given by retrospective analysis of EIT data of post-COVID patients from the UKJ outpatient clinic (planned n=20).
- Number of participants: n=80 subjects
- Procedure for recruiting examination candidates: Addressing UKJ staff/students

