5.1 Conditions for participation in the study

Only adult participants who give written informed consent to participate (subjects) will be included in the study.

Lung-healthy subjects (reference group): Non-smokers, no resting or exertional dyspnoea

Post-COVID patients: presentation at the post-COVID outpatient clinic of the UKJ with subsequent EIT examination (retrospective evaluation of EIT data collected during routine diagnostics).

6. selection of patients

- *Main selection criterion: patients with a post-COVID syndrome who presented at the post-COVID outpatient clinic and lung-healthy subjects who do not smoke.
(retrospective analysis of EIT data of post-COVID patients examined in the post-COVID outpatient clinic of the UKJ and EIT examination of lung-healthy spontaneously breathing subjects from whose EIT data a reference group is to be formed, which does not yet exist).*
- *Female and male patients can be included.*

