6.1 Inclusion criteria

- *Reference group: no resting or exertional dyspnoea, non-smokers*
- *Post-COVID patients: EIT examination performed as part of routine presentation at the post-COVID outpatient clinic.*

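### Age coverage is the reason given for 80 volunteers, but neither recruitment nor the named test secures an age-adjusted comparison

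*Combined protocol and SAP*

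**What the plan says.** The Synopsis (1.3) says that "no formal calculation of the number of patients is calculated". Section 9.3 states that "a subject number of n=80 and patient number of n=20 each is assumed to be sufficient for the investigation of significant differences". The one specific reason for having more volunteers than patients is age coverage. Section 9.3 words it thus: "enough reference values of EIT in the different age groups can be analysed and compared with those of the patients in the age-adjusted comparison". The Synopsis gives the same reason ("enough reference values of EIT in the different age groups").

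The other sections that bear on this are:

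- **Source of volunteers.** Section 4.5: "Procedure for recruiting examination candidates: Addressing UKJ staff/students". Section 7 repeats this source. Neither sets an age quota or matching.
- **Eligibility.** Section 5.1: "Only adult participants who give written informed consent to participate (subjects) will be included in the study". Section 6.1: "Reference group: no resting or exertional dyspnoea, non-smokers". There is no age band and no upper age limit.
- **Patients.** Section 6.1: "Post-COVID patients: EIT examination performed as part of routine presentation at the post-COVID outpatient clinic". Their ages are not given and no age criterion applies.
- **End of recruitment.** Section 4.6 ends the study when the reference group reaches 80, with no condition on age. The timetable in the Synopsis ends it at 20 reference subjects, and section 5 gives 20 as the minimum number of examined subjects.
- **Analysis.** Section 9.4 names the Wilcoxon rank sum test for the pixel matrices and for the distribution of breath volume across the regions of interest (ROIs). It mentions no stratification by age and no age covariate.

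**The concern.** The plan states a purpose for the 80 but provides no means of achieving it, either at recruitment or in the analysis. A convenience sample of staff and students could well be younger than patients attending a post-COVID clinic. If so, and if ROI distribution varies with age, an unadjusted rank sum test mixes the age difference with the disease difference. Adjusting for age removes the bias that the model can capture, but the adjusted comparison then leans on the few volunteers of the patients' ages and is less precise than a count of 80 suggests.

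Both effects can be largely prevented at recruitment. Once 80 unselected volunteers have been examined, a gap can be closed only by recruiting more.

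**Working it through.** **No figure to reproduce.** The plan gives no alpha, power, effect size, standard deviation (SD), age bands or minimum per band, so 80 cannot be re-derived. From the documents come 20 patients and 80 volunteers, a ratio of 80/20 = 4. Everything about age below is assumed.

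**Baseline with matched ages.** In SD units, the standard error (SE) of the group difference is √(1/20 + 1/80) = √0.0625 = 0.25. At two-sided 5% and 80% power (assumed), the detectable difference is (1.960 + 0.842) × 0.25 = 0.70 SD.

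**Assumed age mixes, five bands from youngest to oldest.**

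| | Share (%) | Expected number |
|---|---|---|
| Patients | 10/20/30/25/15 | 2/4/6/5/3 |
| Volunteers, mix A | 50/20/15/10/5 | 40/16/12/8/4 |
| Volunteers, mix B | 70/15/8/5/2 | 56/12/6.4/4/1.6 |

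**Adjustment by band weighting.** Let p be the patients' share and q the volunteers' share in a band. Weighting the volunteers to the patients' age mix gives an effective number n_eff = 80 / Σ(p²/q).

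- Mix A: Σ = 0.020 + 0.200 + 0.600 + 0.625 + 0.450 = 1.895, so n_eff = 42. SE = √(1/20 + 1/42.2) = 0.271, a ratio of 1.09.
- Mix B: Σ = 0.014 + 0.267 + 1.125 + 1.250 + 1.125 = 3.78, so n_eff = 21. SE = √(1/20 + 1/21.2) = 0.312, a ratio of 1.25.

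**Adjustment by a linear age term.** Score the bands 1 to 5 and assume equal residual variance. The variance of the group difference is 1/20 + 1/80 + (difference in mean score)² / (within-group sum of squares). The patients have mean 3.15 and variance 1.4275.

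- Mix A: mean 2.00, variance 1.50. Sum of squares = 80 × 1.50 + 20 × 1.4275 = 148.55. Variance = 0.0625 + 1.15²/148.55 = 0.0714. SE ratio = √(0.0714/0.0625) = 1.07.
- Mix B: mean 1.54, variance 0.9484. Sum of squares = 80 × 0.9484 + 20 × 1.4275 = 104.42. Variance = 0.0625 + 1.61²/104.42 = 0.0873. SE ratio = √(0.0873/0.0625) = 1.18.

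| | n_eff, weighting | SE increase, weighting | SE increase, linear term |
|---|---|---|---|
| Matched | 80 | 0 | 0 |
| Mix A | 42 | 9% | 7% |
| Mix B | 21 | 25% | 18% |

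**A mild mismatch, two bands.** Suppose 50% of patients but 25% of volunteers are in the older band. Then n_eff = 80 / (0.25/0.25 + 0.25/0.75) = 80/1.333 = 60. The SE ratio is √(0.0667/0.0625) = 1.03, and power at 0.70 SD is 77% instead of 80%.

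**No adjustment, as 9.4 reads.** Suppose the older and younger bands differ by a SD in healthy people. The group difference is then shifted by a × (patients' older share − volunteers' older share). The chance of a significant result with no disease effect, by normal approximation with SE 0.25, is:

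| Older share, patients / volunteers | a = 0.3 | a = 0.5 | a = 0.8 |
|---|---|---|---|
| 50% / 25% | 6.0% | 7.9% | 12.6% |
| 50% / 10% | 7.7% | 12.6% | 24.9% |

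For example, with 50% / 10% and a = 0.5 the shift is 0.5 × 0.40 = 0.20 SD, or 0.8 standard errors. If a = 0, the rate stays at 5%.

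**The conflicting count of 20.** If recruitment ended at 20 volunteers, the SE would be √(1/20 + 1/20) = 0.316 and the detectable difference 0.89 SD, before any loss from age mismatch.

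**The case against.** The strongest objection is that no shortage has been shown. The documents give neither the patients' ages nor the volunteers' likely age mix. Hospital staff span the working ages, and the clinic's patients may too. The mixes used here are invented, and the mild one costs almost nothing. All of this stands, and it limits the point to a lack of assurance.

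Three stronger readings are tempting, and the documents do not support them:

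- *The age-adjusted comparison would extrapolate to ages with no volunteers.* This cannot be inferred without the ages. Under mix A every band has volunteers, and even mix B expects one or two in the oldest. What the calculation shows is imprecision.
- *Sixteen to twenty volunteers per band are too few to judge individual patients against a reference range.* Sections 3.1 and 9.4 describe a comparison of groups. No section classifies single patients against an age-specific interval. Matching a fixed 80 would not cure thin bands either.
- *Volunteers must be matched on sex too.* The plan ties the number 80 to age only, and nothing in it shows a problem with sex.

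It can also be said that 9.3 already promises age adjustment. It does, but 9.4 names no method for it, and a plain rank sum test cannot take an age term.

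Finally, part of the loss comes from the choice of adjustment. A linear age term costs less than band weighting, at the price of assuming a straight-line relation with age.

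**Conclusion.** The point holds as a lack of assurance. Age coverage is the plan's own reason for 80 volunteers, yet recruitment, the stopping rule and the named test all ignore age. If volunteers are younger than patients and the ROI distribution depends on age, the comparison in 9.4 is confounded.

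An adjusted comparison would lose precision: about 9% to 25% in SE with band weighting, or 7% to 18% with a linear term, under the two skewed mixes assumed. The loss is about 3% under a mild mismatch and nil if the ages match. The documents cannot say which of these applies. This is a worthwhile and cheap improvement, not a demonstrated failure of the design.

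**What to change.** 1. **Section 4.5.** Select the 20 patients first and take their ages from the routine records. The plan describes the 20 as planned and does not say that they are already chosen. Define age bands from them and frequency-match the planned 80 volunteers at about 4:1. For the patient mix assumed above, that is 8/16/24/20/12. Allow recruitment beyond staff and students for bands that they cannot fill.
2. **Section 4.6.** Make the end of recruitment depend on filling the bands as well as on reaching the total.
3. **Section 9.4.** Name an age-adjusted analysis of the ROI distribution in place of the unadjusted rank sum test. Options are a rank-based or linear regression with age, or a van Elteren test stratified by age band.
4. **Synopsis timetable and section 5.** Reconcile the 20 reference subjects given there with the 80 in 4.4, 4.5, 4.6 and 9.3.

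The cost is a quota table and short edits to these sections, with no change to the planned 80. Older volunteers may take longer to recruit. The reference group would also be tied to the age mix of these patients, which makes it less useful as a general reference for other ages; the protocol should say so.

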9.4 Statistical evaluation

The comparison of the 32x32 pixel matrices of the EIT images [tidal images] and the comparison of the relative distribution of the breath volume across the ROIs is done with the Wilcoxon rank sum test.

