1.5 Visit plan

Table or list with visits and the (study-specific) events that take place, e.g. examinations and measures

Medical history/baseline data collection	+					
Informed consent	+					
Inclusion and exclusion criteria	+					
Randomisation	-					
physical examination	-					
Recording of concomitant medication	+					
Sampling for laboratory ¹	-					
Recording of adverse events	+					

1. Question or background

- conventional diagnostic tools (computed tomography, spirometry, body plethysmography) often fail to detect pathological changes in post-COVID patients with dyspnoea, which makes it difficult for the treating physician to choose an appropriate therapeutic approach
- Post-COVID patients who underwent electroimpedance tomography as part of routine diagnostics have shown clear abnormalities.
- Up to now, there are no reference data from electroimpedance tomography (created regions, distribution of ventilation, non-ventilated areas, minute images, dynamic images, video-based analysis of dynamic images, regional ventilation delay, pendulum air) in spontaneously breathing lung patients, but only EIT data from ventilated patients and non-invasively ventilated subjects. Thus, a reference group is missing.

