2.3 Justification of the treatment and examination procedures

Electroimpedance tomography (EIT) is a non-invasive, radiation-free imaging examination procedure based on the measurement of impedance changes. EIT can be used to visualise regional ventilation based on the electrical conductivity of the thorax at the bedside. This method therefore provides valuable information about the regional ventilation of the lungs.

3. Study objectives

- Aims of the study:
Visualisation of regional ventilation disorders in post-COVID patients compared to a reference group.
- The study will investigate whether there are significant differences between regional ventilation (created regions, distribution of ventilation, non-ventilated areas, minute images, dynamic images, video-based analysis of dynamic images, regional ventilation delay, pendulum air) in post-COVID patients compared to a reference group of lung-healthy subjects.

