3.1 Primary study objective and primary endpoint

- Main question:
Are there significant differences between regional ventilation in post-COVID patients compared to a reference group?
- primary endpoint (target variables):
Relative distribution of the respiratory volume across the so-called regions of interest (ROIs). adjustable in size and arrangement, in which the ventilation ratios represented by the EITcan be measured (regional ventilation of the lung (regional ventilation of the lung: created regions, distribution of ventilation, non ventilated areas, minute images, dynamic images, video-based analysis of dynamic images, regional ventilation delay, pendulum air)

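### Section 9.4 applies an uncorrected, unadjusted Wilcoxon rank sum test to pixel matrices and ROI shares without fixing the unit of analysis, the ROIs or the number of tests, so error control depends on how it is read

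*Combined protocol and SAP*

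**What the plan says.** Section 9.4 (Statistical evaluation) consists of one sentence. It begins "The comparison of the 32x32 pixel matrices of the EIT images [tidal images] and the comparison of the relative distribution of the breath volume" and names the Wilcoxon rank sum test for both, the second being a comparison over ROIs.

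The other places that bear on it are these:

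- **Section 3.1** names the primary endpoint as "Relative distribution of the respiratory volume across the so-called regions of interest (ROIs", describes the ROIs as "adjustable in size and arrangement, in which the ventilation ratios represented by the EITcan be measured", and follows this with a bracket of eight further items (for example minute images, regional ventilation delay and pendulum air). Its main question is "Are there significant differences between regional ventilation in post-COVID patients compared to a reference group".
- **Section 3.2** lists no secondary endpoints, so the pixel comparison is not placed there either.
- **Section 1.3 (Synopsis)** words the main target differently: "Changes in the configuration of the minute image and the regional ventilation delay (RVD) image", together with the RVD diagram and a video-based analysis. ROI shares are not mentioned.
- **Section 3 (Study objectives)** says "The study will investigate whether there are significant differences between regional ventilation", and **Section 9.3** says of the group sizes that the number "is assumed to be sufficient for the investigation of significant differences".
- **The synopsis and Section 9.3** both announce an age-adjusted comparison of patients with the reference group.
- **Section 1 (Question or background)** reports that "Post-COVID patients who underwent electroimpedance tomography as part of routine diagnostics have shown clear abnormalities".

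No section of the text available for review gives a significance level, a number of ROIs, a multiplicity rule or an exploratory label for any test.

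**The concern.** A rank sum test compares two sets of independent values. One 32x32 image supplies 1,024 values per person, and Section 9.4 does not say how they enter the test. Three readings are possible: one test per pixel across persons, one test on all pixels pooled, or one summary value per person. The ROI comparison is open in the same way, because the number of ROIs is not fixed and each ROI could be a separate test.

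The readings have very different error rates. An analyst who follows Section 9.4 faithfully could report a significant region or pixel that arose by chance, and a reader could not tell it from a real group difference. Another analyst, equally faithful to the text, could reach the opposite conclusion from the same data.

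There are two further problems. The plain rank sum test does not deliver the age adjustment promised elsewhere. And because patient images have already been seen, ROIs placed with those images in mind would favour a difference.

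**Working it through.** **Inputs**

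- Group sizes: 20 patients and 80 reference subjects (Section 4.4).
- Pixels per image: 32 × 32 = 1,024 (Section 9.4).
- Interim analyses: none (Sections 4.6 and 9.5), so multiplicity comes only from ROIs, pixels and parameters.
- Significance level: not stated. Two-sided 0.05 per test is assumed.
- Number of ROIs: not stated. 2, 4, 6 and 8 are assumed.

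The plan has no figure to reproduce: the synopsis says no formal sample size calculation was made.

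**1. One uncorrected test per ROI**

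For k independent tests, the chance of at least one false positive is 1 − 0.95^k. ROI shares sum to 100%, so they are not independent. With two ROIs the shares are mirror images and give the same p-value, so there is in effect one test. The simulations used null data with 20 versus 80 persons and Dirichlet shares (10,000 datasets per setting in the main runs).

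| ROIs | 1 − 0.95^k | Simulated, uncorrected | Simulated, Holm or Bonferroni |
|---|---|---|---|
| 2 | not applicable | 5.1-5.3% | one test suffices |
| 4 | 18.5% | 16.4-17.5% | 4.1-4.4% |
| 6 | 26.5% | 24.7-25.3% | 4.0-4.3% |
| 8 | 33.7% | 31.4-32.0% | 4.4-4.6% |

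For four ROIs cut from simulated images, the uncorrected rate was 13.6% (layers) and 14.6% (quadrants). The range for four ROIs is therefore 14-18%.

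**2. One uncorrected test per pixel**

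Expected false-positive pixels = 1,024 × 0.05 = 51.2, whatever the correlation between pixels. Simulation with smoothed images gave means of 50.4-51.6. This assumes that every pixel varies between persons. A pixel that is constant in everyone cannot be significant, so the general figure is 0.05 × the number of varying pixels.

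**3. All pixels pooled as observations**

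This would compare 20 × 1,024 = 20,480 values with 80 × 1,024 = 81,920. If values within a person have correlation ρ, the variance is inflated by about 1 + 1,023ρ, and the true error is about P(|Z| > 1.96/√(1 + 1,023ρ)).

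| Assumed ρ | 1 + 1,023ρ | 1.96/√ | Error by formula | Error by simulation (two sets of runs) |
|---|---|---|---|---|
| 0.01 | 11.23 | 0.585 | 56% | 57%, 52% |
| 0.05 | 52.15 | 0.271 | 79% | 78%, 82% |
| 0.20 | 205.6 | 0.137 | 89% | 90%, 91% |

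These values assume that persons differ in overall pixel level. They would change if each image were normalised first.

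**4. Age left out**

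The ages of the two groups are not given, so this is only an illustration. It assumes three age groups, four ROIs, Holm correction and 4,000 runs per setting. The moderate imbalance was patients 4/7/9 and subjects 40/28/12; the strong one was 2/6/12 and 50/22/8. With an age effect of 0.3-0.5 SD per age group, error without stratification was 6.8-10.7% (moderate) and 12.5-29.5% (strong). With a stratified rank sum test (van Elteren) it was 4.0-5.1% in all nine settings, including balanced ages and no age effect.

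**5. Power cost of correction**

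Detectable shift at 80% power = (z₁₋α/₂ + 0.842) × √[(1/20 + 1/80) ÷ (3/π)].

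- One test at 0.05: (1.960 + 0.842) × 0.25 ÷ 0.977 = 0.72 SD.
- Four tests at 0.0125 each: (2.498 + 0.842) × 0.25 ÷ 0.977 = 0.85 SD.

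Simulation with one of four ROIs shifted, before and after correction on the same definition of power, gave about 0.69 to 0.86 SD for finding any ROI and about 0.73 to 0.88 SD for finding the shifted ROI.

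**The case against.** The strongest reply is that the plan does name one primary endpoint. Section 3.1 opens with the ROI distribution, and Section 9.4 tests that same quantity. The eight-item bracket may only explain what regional ventilation means, since nearly the same list appears in Section 1 (Question or background) and in Section 3. The remark that ROIs are adjustable may describe the device, not an intention to move them. This has force: the bracket should not be counted as eight extra primary endpoints. It still leaves the number and layout of the ROIs open, and the synopsis names a different target.

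A second reply is that Section 9.4 never says one test per pixel. That is correct. The pixel figure belongs to one possible reading, and nothing shows that reading to be the most literal one.

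A third is that Section 9.1 appears only as a heading and Section 9.2 does not appear, so text may have been lost in conversion. That cannot be settled here. The point does not rest on those gaps but on the wording of Sections 3.1 and 9.4 and the synopsis.

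A fourth is that this is a small first comparison with no treatment and no formal sample size. That would excuse modest power. It would justify uncorrected tests only if they were labelled exploratory, and the stated aim is to find significant differences.

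Finally, age imbalance is a confounding question separate from multiplicity, and the age figures rest on invented age mixes. Both statements are true. The adjustment is nevertheless one the plan itself announces, and the test in Section 9.4 does not carry it out.

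**Conclusion.** The point stands in a conditional form: control of chance findings in the only stated analysis is unspecified. It is adequate if one value per person or two ROIs are tested. It is clearly inadequate if four or more ROIs are tested uncorrected, if pixels are tested one by one, or, worst of all, if pixels are pooled across persons. The sizes rest on an assumed two-sided 0.05, assumed ROI counts and assumed within-person correlations.

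A reader might infer that the study is bound to produce false positives, that the sponsor plans 1,024 tests, or that the ROIs will be moved to suit the data. The documents support none of these. They leave the choices open, and at least two natural readings keep the error near 5%. Nor do they show that the groups differ in age; they show only that an announced adjustment is missing from the method.

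The choice should be settled before the groups are compared, because a rule chosen afterwards no longer controls the error.

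**What to change.** In Section 9.4:

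1. State that the person is the unit of analysis and that pixels are never pooled across persons.
2. Fix the number, size and position of the ROIs by a rule that does not depend on patient images, such as a standard layout of equal-sized regions. Fixing them before the comparison is not enough alone, because patient images have already been viewed.
3. Make the ROI comparison the single primary analysis at two-sided 0.05, and align the synopsis and Section 3.1 with it. Use either one prespecified ROI value per person (one test) or all ROIs with Holm or Bonferroni correction.
4. Carry out the announced age adjustment, for example with a rank sum test stratified by prespecified age groups (van Elteren), with a rule for merging groups that are too small.
5. Make the pixel map supportive, with one value per person per pixel and a max-statistic permutation threshold over persons. Label the remaining parameters exploratory.

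**Cost.** No new data are needed, but age groups, a merging rule and a permutation procedure must be written down. Fewer regions and pixels will be called significant. Correcting over four ROIs costs about 0.15-0.17 SD in detectable shift (0.88 − 0.73 and 0.86 − 0.69). A single prespecified value has no multiplicity cost, though it can miss a change that it does not capture. Age stratification adds little if ages are balanced (0.86-0.88 SD with four ROIs and Holm). Under the assumed imbalances the detectable shift is about 0.93 SD (moderate) or 1.05 SD (strong).
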